Radiologic tumor assessment will be performed at baseline, cycle 3 day 1, cycle 5 day 1 and at the end of every 3 cycles beyond cycle 5 (one cycle = 21 days). All patients including those removed from the study due to unacceptable toxicity, will undergo radiologic tumor assessment within 30 days of the time of discontinuation (End of treatment). If a scan is performed within 30 days of end of treatment is available, the previous scan will be accepted. Patients who show disease progression at the first instance could continue to receive the treatment for up to 2 more cycles depending upon the percentage of increase in the tumor. Patients up to 30% increase in tumor burden would be allowed to continue the treatment until the second confirmatory scan if the patient is deriving clinical benefit in the treating Physician's opinion. Patients who continue treatment beyond progression would undergo another confirmatory scan at the end of 2 more cycles and if the progression is confirmed they will be come off the study.

4 Eligibility Criteria

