4.6 Subject Registration

In order to begin the patient registration process, the site must obtain a slot for the candidate patient from Oncoceutics. At the time of receipt of the signed consent form, Oncoceutics medical monitor must be notified via email to initiate eligibility review. The study staff must include de-identified patient source documentation, the completed New Patient Registration Form (provided by Oncoceutics) and a tentative therapy start date. Correspondence from the Sponsor for patient registration approval will be granted within 48 hours of receipt of adequate documentation.

Registration approval will be valid for 7-business days from receipt of approval. If the potential patient is not treated within those 7 business days, a new registration form must be submitted to determine eligibility.

A patient identifier will be assigned at the time of approval. Screening and eligibility MUST be entered into Redcap EDC within 7-business days of screening visit.

5 Treatment Plan

Treatment will be administered on an outpatient basis. Treatment will be administered as described below. Dose delays and modifications should only be done following protocol guidelines described in section 6.0. If treatment delays are more than 14 days due to toxicity study therapy will be discontinued.

Regimen description					
Arm	Agent	Dose	Route	Schedule	Cycle Length
A & B	ONC201	625mg	Oral	Once per week	3 weeks
С	ONC201	625mg	Oral	Twice per week on two	3 weeks
				consecutive days	

5.1 **Treatment Administration**

One treatment cycle will be defined as 21 days, corresponding to 3 doses of ONC201 (i.e., one cycle is 3 weeks) for Arm A and B or 6 doses in Arm C. Beyond cycle 1 week 1 dose(s), ONC201 capsules will be dispensed on day 1 of every cycle thereafter to be taken at home. Patients must complete study drug diary to keep a log of the drug intake. Any unused drug should be returned to the site. Any missed doses should be recorded. At home patients must take the drug as indicated, however if the drug is missed for reasons not related to adverse events +/- 2 days are allowed. The capsules should be swallowed as whole and should not be chewed or broken.

Patients should take designated capsules of ONC201 at approximately the same time on each drug administration. Patients will be instructed to not eat for 2 hours pre and 2 hours post dosing. If the patient vomits after taking ONC201, they should not retake the dose.

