For Arm C: Blood draws taken at baseline (pre-dose), 2 hours ± 15 minutes, 24 ± 1 hours (pre-day 2 dose), 26 ± 2 hours, 48 hours ± 3 hours, 72 hours ± 12 hours, and Day 8 and 15 ± 24 hours following the first administration of ONC201. Blood will also be collected predose for Cycle 2, Cycle 3 and every odd cycle beyond Cycle 3.

Refer to lab manual for collection window of samples. Blood will also be collected at the end of treatment visit for correlative studies. Immune cytokines and effectors will be assessed on serum samples obtained for pharmacodynamic analyses.

Refer to lab manual for Biospecimens processing and handling requirements.

8.3 **Blood for immune cell studies**

Peripheral blood mononuclear cells (PBMCs) will be harvested and investigated for effects of ONC201 on the immune system. One EDTA tube of blood will be collected at the same time points as the red-top tubes are collected: Baseline and 2 hours, 24 hours, 48 hours, and 72 hours after the first dose of ONC201; Cycle 1 Day 8; Cycle 1 Day 15; pre-dose for the first day of cycle 2, cycle 3 and every odd cycle beyond cycle 3. Blood will also be collected at the end of treatment visit for correlative studies. Collection of PBMCs is not required for Arm C.

8.4 **Blood for pharmacokinetics**

The plasma obtained prior to the isolation of PBMCs (see Section 8.3) will be used to determine concentration of ONC201. No additional blood samples will be collected from the patient for these studies. For Arm C, plasma for pharmacokinetics will be collected at baseline (pre-dose), 2 hours \pm 15 minutes, 24 \pm 1 hours (pre-day 2 dose), 26 \pm 2 hours, 48 hours \pm 3 hours, 72 hours \pm 12 hours, and Day 8 and 15 \pm 24 hours following the first administration of ONC201. Blood will also be collected pre-dose for Cycle 2, Cycle 3 and every odd cycle beyond Cycle 3.

9 Study Calendar

Study visits and procedures may be scheduled with a +/-2 business day window except for Screening procedures (-14 days) and neuroimaging (MRI/CT) Screening, Cycle3 and every odd cycle day 1 (+/-7 days). One treatment Cycle is defined as 3 weeks (21 days).

Study Activity	Screening	C1D1	C1D2	C1D3	C1D8	C1D9	C1D10	C1D15	C1D16	C2D1	C2D2	Cycle 3, and every odd cycle, day 1 ⁸	Off- treatment	Follow-up 30 days (+/- 3 days) ⁵	Survival Follow Up (30 +/- 7 days)
Informed Consent	Х														
Medical History	Х														
Inclusion/exclusion criteria	х														
Concurrent meds ¹	х	Х								Х		Х	Х		

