11.1 Response Evaluation Criteria in Solid Tumors (RECIST)

The Response Evaluation Criteria in Solid Tumors (RECIST v 1.1) criteria will be used for objective tumor response assessment. Response assessment would be performed at C3D1, C5D1 and at the end of every 3 cycles beyond cycle 5. All patients, including those removed from the study due to unacceptable toxicity, would undergo radiologic tumor assessment at the time of discontinuation (End of treatment). Patients who show disease progression at the first instance could continue to receive the treatment for up to 2 more cycles if the increase in tumor burden is up to 30%. Patients who continue treatment beyond

progression would undergo another confirmatory scan at the end of 2 more cycles, and if the progression is confirmed, they will be come off the study.

11.2 **Definitions**

Evaluable for adverse events. All patients will be evaluable for adverse events from the time of their first treatment with ONC201.

Evaluable for progression-free survival. All Arm B patients who have received at one dose of ONC201 will be considered evaluable for progress-free survival as the primary endpoint.

Evaluable for objective response. Only those patients who have measurable disease present at baseline, have received at least one cycle of therapy, and have had their disease reevaluated will be considered evaluable for response. These patients will have their response classified according to the definitions stated below. (Note: Patients who exhibit objective disease progression prior to the end of cycle 1 will also be considered evaluable.)

Evaluable Non-Target Disease Response. Patients who have lesions present at baseline that are evaluable but do not meet the definitions of measurable disease, have received at least one cycle of therapy, and have had their disease re-evaluated will be considered evaluable for non-target disease. The response assessment is based on the presence, absence, or unequivocal progression of the lesions.

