11.5.3 Evaluation of Best Overall Response

The best overall response is the best response recorded from the start of the treatment until disease progression/recurrence (taking as reference for progressive disease the smallest measurements recorded since the treatment started). The patient's best response assignment will depend on the achievement of both measurement and confirmation criteria.

Target	Non-Target	New Lesions	Overall	Best Overall Response when					
Lesions	Lesions		Response	Confirmation is Required*					
CR	CR	No	CR	>4 wks. Confirmation**					
CR	Non-CR/Non-PD	No	PR						
CR	Not evaluated	No	≥4 wks. Confirmation**						
PR	Non-CR/Non-PD /not evaluated	No	PR						
SD	Non-CR/Non-PD /not evaluated	No	SD	documented at least once \geq 4 wks. from baseline**					
PD	Any	Yes or No	PD						
Any	PD***	Yes or No	PD	no prior SD, PR or CR					
Any	Any	Yes	PD						
 See RECIST 1.1 manuscript for further details on what is evidence of a new lesion. ** Only for non-randomized trials with response as primary endpoint. *** In exceptional circumstances, unequivocal progression in non-target lesions may be accepted as disease progression. 									
Note : Patients with a global deterioration of health status requiring discontinuation of treatment without objective evidence of disease progression at that time should be reported as " symptomatic deterioration ." Every effort should be made to document the objective progression even after discontinuation of treatment.									

For Patients with Measurable Disease (i.e., Target Disease)

For Patients with Non-Measurable Disease (i.e., Non-Target Disease)

Non-Target Lesions	New Lesions	Overall Response					
CR	No	CR					
Non-CR/non-PD	No	Non-CR/non-PD*					
Not all evaluated	No	not evaluated					
Unequivocal PD	Yes or No	PD					
Any	Yes	PD					
* 'Non-CR/non-PD' is preferred over 'stable disease' for non-target disease since SD is							
increasingly used as an endpoint for assessment of efficacy in some trials so to assign this							
category when no lesions can be measured is not advised							

11.6 **Duration of Response**

Duration of overall response: The duration of overall response is measured from the time measurement criteria are met for CR or PR (whichever is first recorded) until the first date that recurrent or progressive disease is objectively documented (taking as reference for progressive disease the smallest measurements recorded since the treatment started).

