The duration of overall CR is measured from the time measurement criteria are first met for CR until the first date that progressive disease is objectively documented.

Duration of stable disease: Stable disease is measured from the start of the treatment until the criteria for progression are met, taking as reference the smallest measurements recorded since the treatment started, including the baseline measurements.

11.7 **Progression-Free Survival**

Progression-free survival (PFS) is defined as the duration of time from start of treatment to time of progression or death, whichever occurs first. Progression-free survival (PFS) is defined as the time from registration to objective disease progression or death, whichever occurs first. PFS2 will be defined as the percentage of patients who exhibit PFS for >8 weeks (>56 days). Patients who have not progressed or died and are lost to follow up at 2 months will be replaced.

12 Statistical Considerations

12.1 **Primary Endpoint and Interim analyses**

Arm A and C will assess intratumoral drug concentrations and pharmacodynamics. Arm B will assess progression-free survival rate at two month following treatment initiation as primary endpoint. Patients with biopsiable disease may represent a biased subset of the overall target population since some sites of metastases will not be amenable to biopsy and therefore comparing these patients' outcomes to historical controls may not be appropriate. For this reason, only patients in Arm B will be evaluated for the primary endpoint of PFS2.

No interim analyses will be performed for Arm A or C. Pharmacodynamic effects will be evaluated by assessment of tissue biomarkers based on mechanism of action and preclinical tumor cell sensitivity studies. IHC analyses for biomarkers such as ATF4, CHOP, and DR5 will be summarized using descriptive statistics.

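### PFS2 is read at day 56, but no scheduled scan falls between days 49 and 77, and the plan does not say how to count progression first found at cycle 5 day 1

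*Combined protocol and SAP*

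**What the plan says.** - **Endpoint.** Section 11.7: "PFS2 will be defined as the percentage of patients who exhibit PFS for >8 weeks (>56 days". The same section starts the PFS clock once at the start of treatment and once at registration. Section 12.1 counts from treatment initiation.
- **Scans.** Section 3: "Radiologic tumor assessment will be performed at baseline, cycle 3 day 1, cycle 5 day 1 and at the end of every 3 cycles" thereafter. Section 11.1 repeats this schedule. Section 5.1: "One treatment cycle will be defined as 21 days, corresponding to 3 doses of ONC201" in Arms A and B.
- **Window.** Section 9 allows "neuroimaging (MRI/CT) Screening, Cycle3 and every odd cycle day 1 (+/-7 days". The word used is neuroimaging, while the calendar row for tumor assessment is CT/MRI of chest, abdomen and pelvis. Other procedures have ±2 business days.
- **Delays.** Section 5: "If treatment delays are more than 14 days due to toxicity study therapy will be discontinued". Section 6 puts the limit at more than 3 weeks.
- **Off-schedule evidence.** Section 11.1 says that all patients "would undergo radiologic tumor assessment at the time of discontinuation (End of treatment", but Section 3 adds: "If a scan is performed within 30 days of end of treatment is available, the previous scan will be accepted". The note to the response table in 11.5.3 says: "Every effort should be made to document the objective progression even after discontinuation of treatment". It sets no date, and it records decline without objective evidence as symptomatic deterioration.
- **Decision rule.** Section 12.1 tests 40% against 70% at 2 months, continues if at least 5 of 10 succeed, and is positive if at least 14 of 24 succeed. It attributes the 40% to historical controls and names a buparlisib trial as the model. It gives no assessment schedule for either.

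**The concern.** PFS2 is the only endpoint that decides whether Arm B continues and whether ONC201 is taken further. Its landmark lies in a gap in the imaging schedule, so for some patients the score depends on a convention that the plan does not state.

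If progression is dated to the scan that finds it, a patient who progresses on day 50 and is first scanned again on day 84 counts as a success. The endpoint is then in effect a 6-week scan rate with a 2-month label. If progression found at day 84 is instead counted against the drug, the endpoint moves towards a 12-week rate. The cut-offs of 5/10 and 14/24 have their stated error rates only if the success rate measured here is the same quantity as the 40% and 70%.

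**Working it through.** **1. Scan days.** Cycle 3 day 1 is 2 × 21 = 42 days after first dose, and cycle 5 day 1 is 4 × 21 = 84. With ±7 days the windows are days 35–49 and 77–91. If only ±2 business days applies, they are narrower. In both cases day 56 is uncovered.

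**2. The plan's own figures.** Exact two-stage binomial with X1 ~ Bin(10, p) and X2 ~ Bin(14, p):

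P(positive) = Σ over x = 5 to 10 of P(X1 = x) · P(X2 ≥ 14 − x); early stop = P(X1 ≤ 4).

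- p = 0.40: P(positive) 0.0482, early stop 0.6331.
- p = 0.70: P(positive) 0.9009.

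The stated 5%, 90% and 63.3% reproduce.

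**3. Who is unresolved.** Progression at day 42 settles failure. A clean day-84 scan shows that the patient was progression-free at day 56. Only a patient clean at day 42 with progression first found at day 84 is open. The documents give no curve, so assume a constant hazard with 40% and 70% as day-56 rates: S(d) = S(56)^(d/56).

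| | S(42) | S(84) | Unresolved |
|---|---|---|---|
| Null | 0.4^0.75 = 0.503 | 0.4^1.5 = 0.253 | 0.250 |
| Alternative | 0.7^0.75 = 0.765 | 0.7^1.5 = 0.586 | 0.180 |

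Under the null, 0.503 − 0.400 = 0.103 progress between days 42 and 56, and 0.400 − 0.253 = 0.147 between days 56 and 84.

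**4. Progression dated to the detecting scan, 40% a true 8-week rate.** Let c be the share of day 42–56 events caught by day 56 through death or an off-schedule scan. The null success rate is p = 0.503 − c × 0.103.

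| c | p | False-positive rate | Early stop |
|---|---|---|---|
| 0 | 0.503 | 25.8% | 37.0% |
| 0.5 | 0.451 | 12.5% | 50.1% |
| 1 | 0.400 | 4.8% | 63.3% |

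The hazard shape matters. At c = 0.5, a Weibull shape of 0.7 gives 9.7% and a shape of 1.5 gives 18.0%.

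**5. Progression found at day 84 scored as failure.** The success rates are 0.253 and 0.586, so alpha is 0.05% and power 55.9%.

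**6. The 40%/70% taken from 6-week scans with the same dating rule.** The rates measured here are then 0.40 and 0.70, and alpha and power stay at 4.8% and 90.1%.

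**7. How good the backstops are.** Under the 30-day allowance, a clean day-42 scan can stand in for the end-of-treatment scan until day 42 + 30 = 72, which spans the landmark. The documents give no figure from which c could be estimated.

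**8. What can move the first scan.** A 14-day delay puts cycle 3 day 1 at 42 + 14 = day 56, and a 3-week delay at 42 + 21 = day 63, if delays shift the scan; the plan does not say whether they do. On the registration clock, approval is valid for 7 business days (about 9–11 calendar days). A late-window scan at day 49 could then fall 49 + 9 = 58 to 49 + 11 = 60 days after registration.

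**The case against.** The best defence is that the schedule resolves most patients. On the constant-hazard figures about three quarters under the null, and more under the alternative, have a known day-56 status from the two scans alone. Deaths, end-of-treatment scans and the instruction to document progression after discontinuation catch some of the rest. This stands. A reader might infer that no patient's day-56 status can be established; the documents do not support that.

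A reader might also infer that the trial is biased towards a positive result, with a false-positive rate near 26%. That needs three things: progression dated to the detecting scan, a 40% that is a true 8-week rate, and no interval events caught. Section 11.7 contains no dating rule. The text on first objective documentation belongs to duration of response. The opposite convention reverses the direction, and a matching historical schedule removes the effect.

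What the defence does not supply is a rule. Section 11.7 replaces patients lost to follow-up at 2 months, but it says nothing about a patient who is followed and whose progression is first found at cycle 5 day 1.

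**Conclusion.** The point holds in this form: the sole go/no-go endpoint has no scheduled assessment near its landmark, and the plan leaves open the score of patients whose progression is first found at cycle 5 day 1. It also does not say what schedule produced the 40%. Depending on those two unstated items, the same cut-offs can be as designed, liberal (12.5% with half of the interval events caught, 25.8% with none) or very conservative (alpha 0.05%, power 55.9%). The documents settle neither direction nor size.

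The scan days follow from the documents for an undelayed patient counted from treatment initiation. The percentages beyond the plan's own design figures are illustrations under a constant hazard, and other hazard shapes move them. The matter should be fixed before the Arm B data are scored.

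**What to change.** 1. In 11.7 and 12.1, state the assessment schedule behind 40% and 70%. Replace the 56-day sentence with a status rule at one named scheduled scan on that schedule: success is being alive with no RECIST 1.1 progression through that scan, and progression on that scan is a failure. State how a patient without that scan is scored, consistently with the replacement rule. State also that an earlier scan accepted under the 30-day allowance does not count as the landmark assessment.
2. **If these are 8-week rates,** time the first Arm B scan at day 56 (for example days 53–59) in place of cycle 3 day 1. With scans spread evenly over that window, the mean rates are 0.4002 and 0.7001, so the same cut-offs keep alpha at 4.8% and power at 90.1%. No extra scans or patients are needed. The costs are:
   - Day 56 is not a calendar visit.
   - Progression present at week 6 is documented about two weeks later.
   - Arm B imaging differs from Arms A and C.
   - Late drift costs power (87.5% if every scan falls on day 59).
   - Sections 3 and 11.1 tie treatment continuation to the first scan and must be reconciled with the new timing.
3. **If they are 6-week rates,** keep cycle 3 day 1 and the cut-offs, and call the endpoint 6-week PFS. The only cost is the 2-month label.
4. Use one PFS start point in 11.7, matching treatment initiation in 12.1. State whether a treatment delay moves the landmark scan and which imaging window applies to tumor scans.

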5.2.2 Anti-emetic Therapy

There are no restrictions on the use of antiemetic therapy for this trial. Medications to prevent emerging toxicities are permitted as long at their use does not conflict with other guidelines in this protocol.

5.2.3 5.2.3 Other Anticancer or Experimental Drugs

Treatment with other anticancer or experimental drugs is not permitted for patients treated on this protocol.

5.2.4 5.2.4 Palliative and supportive care

All palliative and supportive care necessary for optimal care of the patient, excluding radiation therapy should be provided while on study. Patients requiring radiation therapy for palliation will be removed from the study. Treatment with growth factors is excluded except to treat febrile neutropenia.

5.3 **Duration of Therapy**

In the absence of treatment delays due to adverse events, treatment may continue until one of the following criteria applies:

Confirmed radiographic disease progression. In the absence of clinical progression and occurrence of radiographic progression, patients will have the option to remain on study.

Intercurrent illness that prevents further administration of treatment

Unacceptable adverse events

Patient required > 2 dose reductions

Patient becomes pregnant

Patient decides to withdraw from the study

General or specific changes in the patient's condition that render the patient unacceptable for further treatment in the judgment of the investigator.

5.4 **Duration of Follow up**

All subjects will be followed post-treatment until death, withdrawal of permission to record at least survival data, or subject is lost to follow-up every 30 days (\pm 7 days) after coming off study. When available, tumor imaging will be collected for all patients who accrued to the study and receive at least one dose of ONC201. All subjects will be contacted every 30 days to assess for study-treatment related toxicities, initiation of any new anti-cancer treatments, and survival status. Contact may be performed by a site visit, telephone contact, e-mail, or mail. The date of death, initiation of any new anti-cancer treatments and date of last contact should be documented if this information is available.

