Arm B uses a Simon two-stage mini-max design [27] to evaluate the hypothesis that ONC201 will extend progression-free survival at 2 months beyond historical controls for this disease, as performed for buparlisib (NCT01397877). Historical controls for type II endometrial cancer show the null hypothesis to be 40% progression free survival at 2 months. To show the alternative hypothesis that >70% of patients exhibiting progression-free survival at 2 months with 90% power and an alpha= 5%, 24 evaluable patients are required for this arm. The probability for early termination under the null hypothesis is 63.3%.

An interim futility analysis will be performed for Arm B when the 10 evaluable patients in Arm B are evaluable for PFS2, as defined in section 11.7. In stage 1 of the study, if at least 5 of the first 10 evaluable patients exhibit progress-free survival for at least two months from treatment initiation (as defined in section 11.7), recruitment will be continued until a total of 24 evaluable patients have been enrolled for this arm. In stage two, if at least 14 patients demonstrated progress-free survival at 2 months ONC201 will be considered to have shown sufficient efficacy to warrant further study.

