12.2 Analysis of Secondary/Exploratory Endpoints

All patients enrolled in the study who received at least 1 dose of ONC201 will be evaluated in the safety analysis using descriptive statistics including pre-treatment characteristics and concomitant treatment.

Adverse events and clinical labs will be graded according to NCI CTCAE Version 4.03. For labs without CTC grade definitions, results will be summarized as normal, abnormal or not done. Summary tables will present frequencies of patients experiencing at least one AE categorized by System Organ Class and Preferred Term according to MedDRA terminology. Listings will be prepared for each laboratory measure, and will be structured to permit review of the data by patient as they progress on treatment. Graphic displays and shift tables may be provided, as appropriate, to illustrate the results over time on study. ONC201 dose delays, dose modifications, drug exposure and duration of treatment will be also summarized.

Duration of response and duration of stable disease will be characterized using Kaplan-Meir estimates in the relevant subgroups.

Progression Free Survival (PFS) will be characterized using Kaplan-Meier curves. Median PFS will be calculated along with 95% confidence intervals. Patients who are lost to follow-up (who withdraw from the study prior to evidence of progression or death) will be censored.

12.3 **Reporting and Exclusions**

12.3.1 Evaluation of toxicity:

All patients will be evaluable for toxicity from the time of their first treatment with ONC201. Safety will be assessed by quantifying the toxicities and grades experienced by subjects who have received ONC201, including serious adverse events (SAEs). Other safety endpoints include laboratory safety assessments, vital signs and physical examinations.

A Bayesian method [27] will be used for toxicity monitoring based on the dose-limiting toxicity (DLT) rate. Patients in Arm A and Arm B will be monitored jointly for toxicity. Toxicities will be defined according to the Common Terminology Criteria for Adverse Events (CTCAE) version 4.03. DLT is defined as a clinically significant adverse event or abnormal laboratory value assessed as unrelated to disease progression, intercurrent illness, or concomitant medications and occurring during the first cycle on study that meets any of the following criteria:

- CTCAE grade 3 AST (SGOT) or ALT (SGPT) for > 7 days
- CTCAE grade 4 AST (SGOT) or ALT (SGPT) of any duration

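### PFS2 has no scoring rule for Arm B patients who stop ONC201 early for clinical failure or new therapy without documented progression; as written they become successes or may be replaced

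*Combined protocol and SAP*

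**What the plan says.** Section 2.3 makes the primary endpoint the 2-month PFS rate by RECIST 1.1. Section 11.7 defines PFS twice. One sentence runs from start of treatment to progression or death. The other runs from registration and requires the progression to be objective. It then adds: "PFS2 will be defined as the percentage of patients who exhibit PFS for >8 weeks (>56 days"). Patients without progression or death who are lost to follow-up at 2 months are replaced. Section 11.2 makes every Arm B patient with one dose evaluable for PFS. Section 12.1 applies the Section 11.7 definition to both decision rules: at least 5 of 10, then at least 14 of 24.

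The protocol foresees exits without RECIST progression:

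- Section 11.5.3 gives a separate label to patients with global deterioration "requiring discontinuation of treatment without objective evidence of disease progression at that time should be reported as" symptomatic deterioration, and asks for every effort to document objective progression afterwards.
- Section 5.2.4: "Patients requiring radiation therapy for palliation will be removed from the study".
- Section 5.4 records new anti-cancer treatment and survival every 30 days. On imaging it says: "When available, tumor imaging will be collected for all patients who accrued to the study and receive at least one dose of ONC201".

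Section 3 requires a tumor assessment within 30 days of discontinuation, but adds: "If a scan is performed within 30 days of end of treatment is available, the previous scan will be accepted". For the Kaplan-Meier analysis, Section 12.2 states: "Patients who are lost to follow-up (who withdraw from the study prior to evidence of progression or death) will be censored".

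**The concern.** PFS2 is a yes/no outcome and every dosed Arm B patient is evaluable, so each must be classified. Under the RECIST endpoint, symptomatic deterioration, palliative radiation and a switch of therapy are not events. A patient who leaves for one of these reasons and is alive past day 56 without documented progression therefore satisfies the definition. The other route is replacement: Section 12.2 describes loss to follow-up as withdrawal from the study before progression or death, and Section 11.7 replaces patients who are lost. Both routes raise the observed rate.

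At stake are the two go decisions. With 24 patients, one patient is 4.2% of the arm and can decide whether the count reaches 14. Scoring her as a success may also credit ONC201 with time spent on another treatment.

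**Working it through.** **Step 1: do the scan rules force a classification by day 56?**

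- First on-treatment scan: C3D1 = 2 × 21 + 1 = day 43, with a window of ±7 days (Section 9). The next is C5D1 = 4 × 21 + 1 = day 85. None is scheduled at day 56.
- Discontinuation scan: due up to 30 days after stopping. For a stop on day d it may fall on day d + 30, which is later than day 56 once d > 26. So from about day 27 the scan can be on time and still date progression after day 56.
- Substitution: a scan up to 30 days before the end of treatment is accepted. A patient who stops between days 43 and 56 can use her C3D1 scan and have no later one. For a very early stop, a baseline scan taken b days before the first dose qualifies if d + b ≤ 30. A stop on day 25 needs b ≤ 5; a stop on day 8 needs b ≤ 22. Section 4.5 allows b up to 30.

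Constructed example: a patient stops on day 30 for symptomatic deterioration, starts other therapy on day 40, has her discontinuation scan on day 58 (28 days after stopping, so within the rule), and the scan shows progression. PFS exceeds 56 days and she is a success.

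**Step 2: reproduce the design.** Inputs from Section 12.1: null rate 0.40, alternative 0.70, go rules 5/10 and 14/24, alpha 5%, power 90%.

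P(go | p) = Σ (x = 5 to 10) P(Bin(10, p) = x) × P(Bin(14, p) ≥ 14 − x)

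At p = 0.40 this is 0.0482, with probability of early termination P(Bin(10, 0.40) ≤ 4) = 0.6331. At p = 0.70 it is 0.9009. The stated 63.3%, 90% power and 5% limit all reproduce.

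**Step 3: illustrate the effect.** Let f be the share of all patients who are clinical failures of this kind. Two assumptions are needed, neither supplied by the documents: the value of f, and that the historical 40% counted such patients as failures. Then, at a true rate of 40%:

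- scored as successes: observed rate = 0.40 + f
- replaced: observed rate = 0.40 / (1 − f)

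| f | Rate if scored as success | P(go) | Rate if replaced | P(go) |
|---|---|---|---|---|
| 0 | 0.400 | 0.048 | 0.400 | 0.048 |
| 5% | 0.450 | 0.122 | 0.421 | 0.073 |
| 10% | 0.500 | 0.249 | 0.444 | 0.111 |
| 15% | 0.550 | 0.422 | 0.471 | 0.167 |

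**Step 4: price the remedy.** Counting these patients as failures leaves N, both thresholds and the exact alpha of 0.048 unchanged, provided the 40% already includes them. If the 70% target was set without such failures, the rate under the alternative falls to 0.70 − f, and power falls from 0.90 to 0.78 (f = 5%, rate 0.65) or 0.61 (f = 10%, rate 0.60).

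**The case against.** A reader might infer that these patients can never be failures. The documents do not support that. Section 3 requires a discontinuation assessment for all patients, Section 11.1 repeats it without the substitution clause, and Section 11.5.3 asks for objective progression to be sought after stopping. Progression on a scan or death by day 56 makes the patient a failure. A patient who stops on day 25 owes a scan by day 55 unless an earlier one is accepted, and accepting a pre-treatment scan is a literal reading rather than a stated intention.

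It is also fair that one of the two PFS sentences omits the requirement of objectivity, that no sentence expressly scores these patients as successes, and that the withdrawal wording in Section 12.2 belongs to a secondary analysis. Patients still contacted every 30 days are not lost in the ordinary sense, so replacement is the less natural route.

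The illustration can be challenged too. At f = 10% or 15%, 0.10/0.60 = 1 in 6 or 0.15/0.60 = 1 in 4 of all null failures would have to escape scan and death. If the historical 40% used the same RECIST-only convention, the inflation disappears and a stricter rule would work against the drug.

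What remains is that Section 2.3 ties the endpoint to RECIST, Section 11.2 requires every dosed patient to be classified, and the scan rules let some clinical failures pass day 56 undocumented. The failure rule in Section 12.3.2, which includes unknown status, does not close the gap: it concerns response and applies only after two cycles and re-evaluation.

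**Conclusion.** The point holds in limited form. As the text stands, a dosed Arm B patient who stops before day 57 for symptomatic deterioration, palliative radiation or new therapy, without documented objective progression or death by day 56, counts as a success if followed past that day, or is replaced if Section 12.2's wording is read into Section 11.7. Both outcomes favor ONC201 in both go rules, so this is more than a missing detail.

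The figures in the table should not be read as the trial's actual type I error. They rest on an assumed early-stopping share and on an assumption about the source of the null, of which Section 12.1 says only: "Historical controls for type II endometrial cancer show the null hypothesis to be 40% progression free survival at 2 months". The size of the bias, and whether there is any relative to that control, cannot be settled from the documents. That uncertainty is itself a reason for a rule, because the comparison with 40% is interpretable only if both sides treat these patients alike.

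**What to change.** In Sections 11.7 and 12.1:

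- Keep one PFS definition, with one time origin and one wording of the progression event.
- State that, for PFS2, a dosed Arm B patient is counted as not progression-free, and is not replaced, if before day 57 she stops for clinical progression or symptomatic deterioration, or starts new anti-cancer therapy or palliative radiation, and has no documented progression-free status past day 56.
- Limit loss to follow-up to patients with no further contact.
- Report strict RECIST-only PFS2 as a sensitivity analysis.

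In Section 3, state that a scan taken before the first dose cannot serve as the end-of-treatment tumor assessment. Reconcile Sections 11.2, 11.7, 12.2 and 12.3.2 on who is evaluable, replaced, censored or failed. The sponsor should also confirm how the 40% and 70% rates treat these patients.

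The cost is mainly wording. The reason and date of removal (Section 5.5) and the start of new therapy (Section 5.4) are already to be documented, and N and the thresholds stay as they are. The drawbacks are a less favorable PFS2 rate, some reliance on investigator judgement in an open-label trial, and the loss of power shown above if the 70% target left such failures out. If so, the claim of 24 patients "with 90% power and an alpha= 5%, 24 evaluable patients are required for this arm" would need to be revisited.
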